# **Purpose of Study and Background**

# **Purpose of the Study**

The aim of this investigation is to compare the use of bone marrow aspirate concentrate (BMAC) and allograft versus recombinant human bone morphogenetic protein-2 (BMP) versus the gold standard fusion in subjects undergoing elective lumbar spinal fusion with interbody support. The safety and efficacy of the surgical interventions will be evaluated by assessing fusion status and subjects' quality of life outcomes.

### Rationale

Biologics are almost universally used as an adjunct in spinal fusions for osteoconductive (ability to serve as scaffold for bone growth), osteoinductive (ability to stimulate bone growing cells), and osteogenic (bone growth cells creating new bone) effects. However, the use of BMP is marginally very expensive and has well documented complications such as cancer, wound complication, and increased immediate post-operative pain. BMP is a commonly used adjunct for minimally invasive surgeries of the lumbar spine for its osteoconductive, osteinductive, and osteogenic effects without the need for autologous bone graft. Recent studies, specifically the study by [name]. using BMAC with allograft, and the study by Gan et al. using BMAC with beta-tricalcium phosphate during spinal fusion procedures have produced positive results comparable to BMP results. In addition, several recent studies using BMAC to treat bone non-unions and osteonecrosis (abnormal bone death) have been positive. Therefore, it is believed that BMAC with allograft has the same osteoconductive, osteoinductive, and osteogenic effects as BMP without including the same complications. Previous research conducted at our own institution has demonstrated clear efficacy in the usage of bone marrow aspiration and concentration for the treatment of high risk adult spinal deformity patients relative to iliac crest, in a randomized manner. This has been tremendously helpful in our attempt to reduce inefficiencies in the cost of patient. This study intends to further investigate and compare the efficacy and long term effects of anterior lumbar spinal fusions with BMAC and allograft to that of BMP in 2-4 level lumbar spine surgical cases. This study also attempts to enhance our understanding of the cellular mechanisms that correlate with outcomes, a point of deficiency in previous studies, by adding a cellular analysis component. Use of BMAC and allograft may be an alternative to BMP that will limit BMP's increased price, known increase of complications, and foreign antibodies. It is anticipated that there will be an increase in minimally invasive spine surgeries for lumbar degenerative disease which will expand the role and use of biologics due to suboptimal successful fusion rates without their usage. This increase in minimally invasive surgery has been reflected in the busy practices of the coinvestigators of this trial who wish to study the comparative efficacy of the 2 main biologics currently in use as their standard practice.

For validity and to provide reference the 2 main biologics will be controlled with the auto graft gold standard fusion. In some applications, such as intervertebral disc fusion in the cervical and lumbar spine, allografts with internal fixation have rivaled the results of autogenous bone grafts. Studies by Bishop et al., Martin et al., and Zdeblick and Ducker have shown that using allograft bone in the anterior cervical spine during fusions is just as adequate as autograft bone. In addition, Savolainen et al. observed similar rates of fusion in autograft and allograft. Also, in the lumbar spine, anterior femoral ring allografts have been very successful when posterior instrumentation is

PI: [name]

used. Also, posterior spinal fusions for scoliosis in adolescents have similar rates of fusion when comparing allograft and autograft. Still further comparison is needed and a study comparing autograft as a control in BMAC vs. BMP will fill a gap in the literature.

The high expense and limited indication of BMP products makes it necessary to apply for prior authorization from insurance companies of these products for usage by insurance companies. For the purposes of this study, standard of care in all aspects will be followed, and pre-operative authorization for use of BMP as well as BMAC will be obtained from insurance companies prior to the day of surgery. If authorization cannot be obtained prior to the day of surgery the subject enrolled will be counted as a screen fail. While both of these products are currently approved for use by the NYU/HJD operating room product and pricing committees, through the conduction of this research we will also be working with the NYULMC supply chain management team in vetting and determining the clinical cost effectiveness of these biologics.

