## Conclusions of previous clinical models

BMP has been used since 2002 in the lumbar spine to promote bony fusion since its approval by the FDA for use in anterior lumbar interbody fusion, and is now approved for use in posterior and transforaminal approaches. BMP augment bony growth is promoting MSC and osteoprogenitor cell differentiation into osteoblasts, which is very similar to BMAC. In a 2015 systematic review of lumbar fusion rates with the use of rhBMP-2, Galimberti et al showed interbody lumbar fusion rates ranging from 97.8-93.6%. However, as detailed in a review of randomized clinic trials by Chrastil et al in 2013, despite high fusion rates, there may complications associated with BMP such as heterotopic ossification, radiculitis, and endplate osteolysis. While usage of BMP is attractive for avoiding autologous grafting—decreasing operative times, blood loss, avoiding donor site morbidity, and allowing for biologics in older, more morbid patients that may have a limited autograft supply.

Previous reports by Connolly et al., Gangji et al., Hernigou et al., and Gessmann et al. have also shown that high concentrations of adult stem cells from iliac crest bone marrow can enhance the rate and amount of bone formation. The authors report that technology that quickly and easily concentrates bone marrow stem cells 3 to 6 times harvested baseline concentrations makes practical the use of adult bone marrow stem cells in a spinal fusion. In a study by Gan et al., they found a 95% successful spinal fusion rate when 252 mL BMA harvested from the iliac crest was

PI: [name]

concentrated peri-operatively down to 45 mL enriched suspension. In contrast, the historical autograft fusion success rate ranges between 65-95%.

These studies conclude that both BMP and BMAC mimic and supplement the body's natural response to trauma by stimulating vasculogenesis and tissue regeneration. BMAC contains many cell types, while BMP contains only one, the question of superiority between the two methods of bone healing/remodeling stimulation is unanswered. As BMAC is autologous, there are no immuno-rejection side-effects or concerns regarding disease transmission.

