  - 1. Pre-operative measures: narcotic usage, and health-related quality of life measures previously definedIntra-operative measures: intra-operative and perioperative blood loss, length of stay, complications
  - 2. Post-operative measures: fusion status at 1 year via CT scan, and health-related quality of life measures previously defined, length of stay, radiological outcomes, complications
- The patient and reviewer [of the clinical outcomes as well as the radiographic analysis postoperatively] will be blinded to the patient's treatment.

All materials procured from Harvest® BMAC System is FDA approved:

- Collection of Bone Marrow Aspirate Concentration (autologous adult stem cells) for Fusion
  - Bone Marrow Aspirate (BMA) will be aspirated from the anterior iliac crests using an 11 gauge 5 side-hole Jamshidi needle and a 60 mL syringe flushed with heparinized saline. Following a midline incision, the needle will be directed at about 30° to the vertical and parallel to the plane of the crest and inserted to a depth of approximately 5 to 8 cm (Figure 1). 1 mL will be sent for cellular analysis.

Figure 1

- Sixty mL of BMA will be aspirated while rotating and slowly withdrawing the needle toward the cortex. This step will be repeated on the contralateral ileum for a total of **60**, **120**, **or 180** mL of BMA. The BMA is then pooled into a blood bag containing Anticoagulant Citrate Dextrose Solution (ACD-A).
- The BMA will then be placed into the SmartPrep® Bone Marrow Concentrate (BMACTM, Harvest Technologies Corp., Plymouth, MA) system and concentrated in 15 minutes to a final volume of **10**, **20**, **or 30 mL**.
- The BMAC will then be combined with packed allograft cancellous bone chips using the Graft Delivery Pack (GDP, Harvest Technologies Corp.) yielding two or three 10 mL surgeon constructed bone logs (Figure 2). The allograft bone will be obtained routinely from the bone bank in the operating suite.

PI: [name]

Figure 2

• The allograft logs will be placed in the lateral gutter and interbody cages.

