### **Adverse Events/Risks**

Although BMP is a frequently performed surgical procedure with easy use, complications with BMP, as with all surgeries with and without BMP of this type, are common and well documented in literature including, but not limited to, tumorigenesis, infections, seroma formation, or osteolysis. As the use of BMP to augment spinal instrumentation and fusion is a standard procedure, adverse events will be managed using standard surgical protocols.

PI: [name]

The use of allograft as a graft extender has become an acceptable practice especially in fusions employing interbody. The advantages of using of allograft rather than BMP during spinal fusion include decreased cost, similar structural support, and lack of BMP associated complications.

. In general, the use of autograft versus allograft should be balanced with donor site morbidity (pain, bleeding, infection) on the one hand, and the risk of pseudoarthrosis as well as the possibility of revision surgery on the other.

The disadvantages for allograft utilization include a higher potential for transmission of disease or infection, unavailability in some countries, immunogenicity with an inflammatory response, slower incorporation, and possible graft collapse. Allograft cancellous bone invokes a larger inflammatory response when compared to cortical allograft bone due to the larger surface area available for an immune response. In addition, cortical allografts are incorporated more slowly and to a lesser degree prior to remodeling than other allograft bone. In general, allograft is incorporated slower and less completely with decreased vascularization and osteoconduction than its autograft counterpart.

The safety of autologous bone marrow transplantation is quite good. Many surgeons now use bone marrow because of its biological value and low risk. One of the authors in the study by Hernigou et al. (P. Hernigou) has clinical experience with aspiration of bone marrow in more than 1000 patients, in which no complications were encountered. In this study, bone marrow aspirate will be collected in a minimally-invasive manner.

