### Investigation schedule and follow-up

Data will be collected pre-operatively regarding individual patient demographics, radiographic images, laboratory values, and the surgical procedure to be performed. These data will be recorded onto a de-identified data collection sheet by the researchers. The patient data sheets will then be entered into a protected electronic database, while the data sheets will be stored as a back-up until the study is complete. Once the completed database is analyzed and summarized, the results will be presented to the involved participants without any identifiable patient information. A Delegation of Duties log will be prepared and maintained in the study regulatory binder.

A separate surgeon and radiologist will be performing the radiographic analysis and an office medical assistant will have the patients fill out questionnaires and record any complications pertinent to the study. Follow-up will be the investigators' routine follow-up, which is 6 weeks, 3 months, 6 months, 1 year, and 2 years post-op.

PI: [name]

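### The BMP risks that motivate the trial are captured only as undefined complications: early pain is not scheduled, post-operative narcotic use has no time point, and the blinded CT reading is defined for fusion alone

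*Combined protocol and SAP*

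**What the plan says.** All references are to the combined protocol and SAP.

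**Risks named.** The Rationale says that BMP "has well documented complications such as cancer, wound complication, and increased immediate post-operative pain", and presents BMAC with allograft as a way to get the same biological effect without those complications. Conclusions of previous clinical models adds "heterotopic ossification, radiculitis, and endplate osteolysis". Adverse Events/Risks adds "tumorigenesis, infections, seroma formation, or osteolysis".

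**How safety is to be judged.** Purpose of the Study: "The safety and efficacy of the surgical interventions will be evaluated by assessing fusion status and subjects' quality of life outcomes". Complications are not mentioned there.

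**What is collected, and when.**
- The outcome list under Intervention has "Pre-operative measures: narcotic usage, and health-related quality of life measures". Its peri-operative items are blood loss, length of stay and complications. Its post-operative items are CT fusion at 1 year, quality of life, length of stay, radiological outcomes and complications.
- Standard of Care vs. Research Procedures lists narcotic usage again, without a time.
- Investigation schedule and follow-up sets the visits, "which is 6 weeks, 3 months, 6 months, 1 year, and 2 years post-op". Case Report Forms goes from the pre-operative visit straight to 6 weeks.
- Aim 1 of Data Analysis defines the CT reading as fusion status by an independent radiologist. It names t-tests on change scores and a regression on reaching MCID, and no comparison of complications.
- Data Monitoring, item 3, has the investigators look for adverse events by examination and by reviewing x-rays and CT scans. Item 2 says that the principal investigator knows the group assignment.

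**The concern.** The argument for BMAC has two halves: fusion comparable to BMP, and fewer of BMP's complications. The first half has a dated endpoint with a blinded reader. The second has no defined endpoint.

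Two of the named risks need a deliberate measurement. Immediate post-operative pain is over, or blurred, by 6 weeks. Heterotopic ossification and endplate osteolysis can be present on CT without symptoms, so they are recorded dependably only if a reader is asked to look for them. The hypothesis is that the groups will be similar. If these effects are not systematically sought, finding no difference in them says little about whether one exists.

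**Working it through.** The plan states no figure for this point, and no sample size was set for a safety outcome. The main check is therefore a comparison of passages.

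**1. Each motivating risk against its planned measurement**

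| Risk | Named in | Planned measurement |
|---|---|---|
| Immediate post-operative pain | Rationale | VAS before surgery, then first at 6 weeks; no in-hospital or discharge score listed |
| Narcotic use (a marker of pain) | Listed as an outcome | Pre-operative in the outcome list; untimed under Standard of Care |
| Heterotopic ossification, endplate osteolysis | Conclusions of previous clinical models; osteolysis also in Adverse Events/Risks | No blinded criteria; unblinded adverse-event review of images; radiological outcomes listed without content |
| Wound complication, infection, seroma, radiculitis, tumour | Rationale; Conclusions of previous clinical models; Adverse Events/Risks | Recordable as complications or adverse events; no definitions or checklist |

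The last row is covered, though loosely. The first three are where the gap lies.

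**2. How many patients it concerns**

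Inputs from Sample Size Analysis: 60 enrolled, 20 per arm, 85% completion.
- Early pain: no scheduled score from surgery to 6 weeks in all 60.
- One-year CT: 60 × 0.85 = 51 scans, or 20 × 0.85 = 17 per arm. The number is lower if patients decline the CT, as Costs to the Subject allows.

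**3. What event counts could show**

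With no events among n patients, the exact one-sided 95% upper bound on the risk is 1 − 0.05^(1/n).
- n = 20: 1 − 0.05^(1/20) = 13.9%
- n = 17: 1 − 0.05^(1/17) = 16.2%

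Smallest split against zero that reaches two-sided Fisher p ≤ 0.05:
- 20 per arm, 5 v 0: p = 2 × C(20,5)/C(40,5) = 2 × 15,504/658,008 = 0.047. With 4 v 0: 2 × 4,845/91,390 = 0.106.
- 17 per arm, 5 v 0: p = 2 × C(17,5)/C(34,5) = 2 × 6,188/278,256 = 0.044.

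The protocol gives no arm-specific rates for these effects. For an assumed 10% v 30%, exact Fisher power is 24% at 20 per arm and 19% at 17; 80% power would need 62 per arm (normal approximation). Better ascertainment would make the counts interpretable, but it would not make them confirmatory.

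**The case against.** The best opposing case is that the plan does look for harm. Complications are both a peri-operative and a post-operative outcome. Adverse events are graded, reviewed monthly and tied to an action threshold. Item 3 of Data Monitoring says that all identified events go to the principal investigator and coordinator. Item 2 has a safety board consulted on identifying and grading events, and gives a blinded independent reviewer the task of adjudicating outcomes.

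This stands, and it rules out several stronger readings that a reader might infer:
- *That the CT is read only for fusion.* Item 3 has CT scans reviewed for adverse events, and radiological outcomes are listed separately from fusion. What is missing is written criteria and a blinded reading of anything but fusion.
- *That the BMP risks go unmeasured.* A wound problem, an infection or a diagnosed tumour would be reportable.
- *That narcotic use is recorded only before surgery.* The untimed listing leaves this open, and the fields of the follow-up forms are not reproduced, so absence cannot be shown.
- *That the result is biased toward no difference.* Missed events could hide a difference, but unblinded investigators who expect BMP complications could equally over-report them. The direction is not shown.

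It can also be said that early pain is outside the scope, because the hypothesis is set at 24 months and the Rationale speaks of long-term effects. That argues against making it a primary outcome. It does not explain naming the risk as a reason for the trial, promising a safety evaluation, and scheduling nothing that could address it.

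Finally, early pain would be hard to attribute. Controls commonly have iliac crest harvest, and patients may know their arm. This limits interpretation, but is no reason to leave the data in the chart.

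**Conclusion.** The point holds as a cheap improvement, not as a flaw in the primary comparison. Followed as written, the trial has no scheduled measure with which to compare early pain in its 60 patients. It also leaves CT-visible BMP effects without symptoms, on about 51 expected one-year scans, to an adverse-event review without criteria by investigators who know the arm. A statement of similar safety would be uninformative on both counts. No claim is made about the size or direction of any difference between arms.

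This rests on two assumptions: that the outcome lists and visit schedule are complete as published, and that 85% completion applies at the 1-year CT. If the unpublished forms already capture timed narcotic use or discharge pain, that part reduces to writing it into the outcome list.

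**What to change.** 1. Add in-hospital pain scores and narcotic use from surgery to discharge, and narcotic use at each follow-up visit, as secondary outcomes by arm. Take the in-hospital data from the hospital chart, which Data Storage and Confidentiality already names as source.
2. Have the planned blinded reader score heterotopic ossification and endplate osteolysis, yes or no per level, on the same 1-year CT, with the criteria written down beforehand.
3. Amend Purpose of the Study so that the safety evaluation includes complications. Report patient counts by arm with exact confidence intervals, labelled descriptive.

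**Cost.** A few form fields, chart abstraction for up to 60 patients and some extra reading time per CT. No added scan, visit or reader is needed, and no care changes.

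**Limits to state.** In-hospital pain is routine-care data, confounded by iliac crest harvest in the control arm and by patients knowing their arm. On the latter the protocol contradicts itself: one statement under Intervention and the Blinding section say that patients are not blinded, while another statement under Intervention says that they are. These must be reconciled. With 17 to 20 per arm, the binary events will not support a claim of equivalence or of difference.

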### **Human Subject (Inclusion/Exclusion Criteria)**

#### **Inclusion criteria:**

- 1. Must be 18 years old or older
- 2. Scheduled for elective posterior or anterior and posterior spinal fusion of the lumbar spine with or without anterior interbody support
- 3. Failed at least 6 weeks of conservative care
- 4. ODI v2.1 score > 30%
- 5. No contraindication to BMAC (as per manufacturer)
- 6. Signed consent form

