### Intra-operative exclusion

1. Any change in the surgical procedure PRIOR to surgery that violates the inclusion/exclusion criteria.

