## **BMAC** dosing estimate for the lumbar spine

- If using Harvest Graft Delivery Kit:
  - o 1-level fusion: 10 cc of BMAC from 60 cc of BMA (roughly 10 cc of graft)
  - o 2-level fusion: 20 cc of BMAC from 120 cc of BMA
  - o 3-level fusion: 20 cc of BMAC from 120 cc of BMA
  - o 4-level fusion: 180 cc kit
  - o 5-level fusion: 240 cc kit
    - BMAC to graft ratio will be 1:1
- If not using Harvest Graft Delivery Kit:
  - Volume of BMAC will be slightly increased (some BMAC will not get directly into hydrating the graft as the BMAC would get lost in the hydration process and left in mixing bowls)

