#### rhBMP-2 Fusion

- Two mL of BMA will be aspirated in identical procedure to the BMAC group for comparison of aspirate quality.
- For patients selected to receive BMP, 12 mL BMP will be applied at the surgical site of the interbody fusion using a collagen sponge following manufacturer's directions.
- BMP kit use per level:
  - o 1 Level Fusion: Extra small kit (1.4 cc)
  - o 2 Level Fusion: Small Kit (2.8cc)
  - o 3 Level Fusion: (4.2 cc)
  - o 4 Level Fusion: Medium Kit (5.6cc)
  - o 5 Level Fusion: (7.0 cc)

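### Graft dosing contradicts itself: a flat 12 mL of BMP against a table of 1.4 to 7.0 cc, and a BMAC procedure that does not fit its own dosing list at one and five levels

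*Combined protocol and SAP*

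**What the plan says.** **BMP arm.** The rhBMP-2 Fusion section states that "12 mL BMP will be applied at the surgical site of the interbody fusion", on a collagen sponge and as the manufacturer directs. Directly below is a list by number of levels. It begins "1 Level Fusion: Extra small kit (1.4 cc" and rises through 2.8, 4.2 and 5.6 cc to 7.0 cc at five levels.

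**BMAC arm.** The collection procedure under Intervention draws 60 mL of aspirate and repeats the draw on the other side. It allows totals of 60, 120 or 180 mL, concentrated to 10, 20 or 30 mL. The concentrate is then combined with allograft chips, "yielding two or three 10 mL surgeon constructed bone logs". The section BMAC dosing estimate for the lumbar spine gives volumes by level. Its first row is "1-level fusion: 10 cc of BMAC from 60 cc of BMA (roughly 10 cc of graft" and its last is "5-level fusion: 240 cc kit". It also sets concentrate to graft at 1:1.

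**Number of levels.** The Rationale says the comparison will be made "in 2-4 level lumbar spine surgical cases". The relevant inclusion criterion is "Scheduled for elective posterior or anterior and posterior spinal fusion of the lumbar spine", with no minimum or maximum number of levels, and none of the twenty exclusions supplies one. The intra-operative exclusion covers only "Any change in the surgical procedure PRIOR to surgery that violates the inclusion/exclusion criteria", so it adds no level limit of its own.

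**The concern.** The graft is the only thing that is meant to differ between the arms, so its dose has to be stated once and be executable. As written, two surgeons could implant different amounts of BMP in identical patients and both claim to follow the protocol. A five-level BMAC patient cannot be treated in line with both the procedure and the dosing list.

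The BMP dose also bears on safety. The Rationale and the Adverse Events/Risks section attribute complications to BMP, and Criteria for Action ties stopping to complication rates above 10-15%. If the dose is ambiguous, a complication rate in that arm is hard to interpret.

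The level range matters less. The Rationale describes a narrower group than the one that can be enrolled, and the two statements should agree.

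**Working it through.** **1. BMP (inputs: rhBMP-2 Fusion).** Ratio = 12 divided by the table volume.

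| Levels | Table (cc) | 12 / table |
|---|---|---|
| 1 | 1.4 | 8.6 |
| 2 | 2.8 | 4.3 |
| 3 | 4.2 | 2.9 |
| 4 | 5.6 | 2.1 |
| 5 | 7.0 | 1.7 |

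Every row works out at 1.4 cc per level. No row reaches 12. Reading the 12 mL as a per-level dose does not reconcile them: 12 / 1.4 = 8.6 at every level.

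**2. BMAC (inputs: the procedure under Intervention, and the dosing estimate).** The procedure's concentration ratio is 60/10 = 120/20 = 180/30 = 6. At 1:1, with about 10 cc of graft from 10 cc of concentrate, the number of logs is concentrate / 10.

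| Levels | List: aspirate (cc) | Concentrate (cc) | 10 mL logs | Fits the procedure? |
|---|---|---|---|---|
| 1 | 60 | 10 | 1 | Volumes yes, logs no |
| 2 | 120 | 20 | 2 | Yes |
| 3 | 120 | 20 | 2 | Yes |
| 4 | 180 kit | 30* | 3* | Yes |
| 5 | 240 kit | 40* | 4* | No |

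*The list gives only a kit size here. These entries assume that the 6:1 ratio holds (180/6 = 30, 240/6 = 40).

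Five levels: the list asks for 240 cc and the procedure stops at 180 mL, a gap of 60 mL on the stated figures. On the 6:1 assumption the concentrate would be 40 mL against a cap of 30 mL.

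One level: 60 mL and 10 mL appear in both places. Two things do not fit.
- Two or three logs is 20 to 30 mL, against roughly 10 cc of graft.
- A 60 mL draw that is always repeated on the other side gives 60 + 60 = 120 mL, not 60.

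**3. Level range.** The Rationale says two to four levels. The inclusion and exclusion criteria set no limit. Both dosing lists have rows for one, two, three, four and five levels. Control Fusion doses by level without a cap. The BMAC conflicts fall at one and five levels, the two dosed levels outside the Rationale's range. The BMP conflict is present at all five.

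**The case against.** The best reply is that the text can be read charitably.

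- **BMP.** The section defers to the manufacturer's directions, Intervention defers to the approved labels, and an appendix of labelling is cited but is not in the text supplied. That appendix may settle the volume. This is why a label check belongs in the fix. It does not make two incompatible volumes in one section acceptable. A reader might infer that patients will be overdosed by up to 8.6 times. The documents do not support that, because they do not show which figure the surgeon will use.
- **One-level BMAC.** The aspirate and concentrate volumes agree, and the 1:1 ratio points to one log. The likeliest explanation is that one log was left out of the wording. That stands. A reader might infer that one-level patients will get two to three times the intended graft, but the procedure does not prescribe 20 to 30 mL specifically for them.
- **Five-level BMAC.** The list is headed an estimate. Research Procedures classes the dosing as specific to the research, but it points to a Procedures section, and no section has that title. A reader might infer a 25% shortfall (30 against 40 mL). That rests entirely on extrapolating the 6:1 ratio. The list has no constant dose per level either: its three-level row gives 20/3 = 6.7 mL per level, and the cap at five levels gives 30/5 = 6.0, about 10% lower. What remains is the direct clash of 240 cc with 180 mL.
- **Level range.** The two-to-four figure appears once, in narrative. The purpose, hypothesis, objective and design sections carry no range. The same Rationale sentence says anterior fusion, which eligibility does not follow either. This objection largely stands, and the point is therefore a lesser one.

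**Conclusion.** The dosing text is wrong as written and should be corrected. The BMP conflict is the most important: 12 mL is 1.7 to 8.6 times the tabulated volume, and this follows from the stated figures without any assumption. The five-level BMAC conflict (240 cc against a maximum of 180 mL) is also direct. Only its size in concentrate, about 40 against 30 mL, depends on assuming 6:1. The one-level conflict is narrow and is confined to the log count and the contralateral draw. The mismatch between the Rationale and eligibility is a matter of consistency.

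A reader might go further and infer that a mix of levels threatens the primary fusion comparison. The documents do not support putting a size on that. They give no distribution of levels, and they do not say whether the fusion rates they cite (94% for BMP-2 and 85% for bone marrow aspirate, in Criteria for Action) are per patient or per level. No stratification or covariate follows from this point.

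**What to change.** 1. In rhBMP-2 Fusion, delete the flat 12 mL and let the per-level table govern, after the sponsor has checked the table against the product label.
2. Keep one to five levels and correct the Rationale to match.
3. In the BMAC procedure under Intervention:
   - make the contralateral draw conditional on needing more than 60 mL;
   - allow one log at one level;
   - add the 240 cc kit for five levels, with the concentrate volume confirmed by the sponsor (about 40 mL if 6:1 holds, which is an assumption).
4. Report the number of levels by arm, using the surgical procedure data already collected under Investigation schedule and follow-up.

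The cost is a few wording edits and the sponsor's confirmation of the volumes. Keeping one to five levels excludes no patient who is now eligible, and the sample size and analysis are unchanged.
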